6.6.2. Supplementary Analyses for the Primary Efficacy Analysis

As a supplementary analysis, Clopper-Pearson 95% CI for the difference between 2 proportions will be calculated using the asymptotic Wald method. Sample SAS codes of comparing each dosing regimen of izokibep to the combined placebo group is given as following are:

```
ods output RiskDiffCol2= ;
proc freq ;
tables treatment*response / riskdiff(cl=wald);
weight count / zeros;
run;
```

This analysis will assess whether stratification impacted the conclusions.

For Part B, supplementary analyses using other assumptions about ICEs and other ways to address missing data will also be reported. These will be defined before the database is locked and treatment assignments are unblinded.

Worst Case Scenario Imputation: All subjects with prohibited medication will be imputed as NR in active arms, and as Responder in the placebo arm. A stratified test will be used with the actual randomization factors as strata.

Lesional incision and intralesional steroid: An analysis imputing subjects as nonresponders if any lesion received lesional incision and drainage or intralesional steroid injection will be reported. This analysis will match the primary analysis, except that subjects who received any (one or more) such treatments will be imputed as non-responders in this analysis (instead of only continuing to count the lesion as present, as in the primary analysis).

Tipping point analysis: A tipping point analysis will be performed in order to evaluate the robustness of the results of the primary analysis. This analysis will use simulations to assess the impact of different response rates in subjects with missing primary endpoint data, and how different the response rates must be to change the conclusions of the study. The tipping point analysis will impute mean response rates in the two groups. Imputed response rates will be based on the response rates among subjects with observed primary endpoint data at week 16. Sets of imputed mean response rates will include the observed response rates ($\hat{\pi}_{ABY}$, $\hat{\pi}_{PBO}$), and rates that differ in increments of ± 0.02 , adjusted independently in each arm. For each set of imputed mean response rates, 1000 simulations will be reported. Within each simulation, a random number mechanism will be used to assign each subject who is missing the primary endpoint at week 16 to either response or non-response, with response probability of the mean response rate for that treatment arm in that simulation. The primary stratified analysis will be reported on each simulated study, and the probability that the null hypothesis of equal response rates is rejected will be reported for each set of 1000 imputed response rates. A graphical output will summarize the rejection probability for various sets of response, with different shadings representing probabilities of >95%, 80-95%, 50-80%, 20-50% and $\leq 20\%$.

Multiple Imputation: Multiple imputation⁵ will be implemented to replace missing endpoint data using multiple draws from a posterior predictive distribution estimated from the placebo group only. First, a monotone missingness pattern will be enforced using Markov Chain Monte Carlo (MCMC). The MCMC process will use predictor variables of baseline abscess count (continuous), baseline inflammatory nodule count (continuous), baseline draining fistula count (continuous), age (continuous), baseline BMI (continuous) for nonmonotone missingness at Week 4 (missing at Week 4 but available at a later timepoint). MCMC predictors in the regression model for missing values after Week 4 will be all of these variables, plus counts of abscess (continuous), inflammatory nodule (continuous), and

draining fistula (continuous) at prior scheduled assessments. After monotone missingness is enforced, missing HiSCR75 at Week 4, 8, 12, and 16 will be imputed, assuming monotone missingness pattern. Any missing HiSCR75 will be imputed by first imputing components of the AN count (abscess and inflammatory nodules) and draining fistula count, then assigning HiSCR75 status from the imputed values. Predictors in the regression model for missing values at Week 4 will be baseline Hurley stage (II/III), baseline abscess count (continuous), baseline inflammatory nodule count (continuous), baseline draining fistula count (continuous), sex (male/female), race (white/non-white), age (continuous), BMI (continuous) and Prior Biologic/Janus Kinase (JAK) Inhibitor Use for HS (yes/no). Predictors in the regression model for missing values after Week 4 will be all of these variables, plus counts of abscess (continuous), inflammatory nodule (continuous), and draining fistula (continuous) at prior scheduled assessments. Missing HiSCR75 values in both the placebo group and two izokibep groups will be imputed using observed data from the placebo group only. Data will be processed sequentially by repeatedly calling SAS® PROC MI to impute missing outcomes at Week 4, 8, 12, and 16. A total of 100 imputations will be imputed to form the complete data set with a pre-specified seed (3617627) to ensure reproducibility. These multiple imputed data sets are then analyzed by using the same method for the primary analysis for complete data as specified in Section 6.6.1. The final inference on treatment difference is conducted from the multiple datasets using Rubin's combining rules⁶. Other imputation, fully conditional specification method may be implemented if the multiple imputation model does not converge. If imputation is not possible due to sparseness of data for certain predictor variables, that predictor variable will be collapsed. If the predictor variable is race, race will be first collapsed into three categories (Black, White and Other) and, if further collapsing is necessary, into two categories (Black and Other). If the predictor variable is other than race, that predictor variable will be collapsed into a single category, in essence removing that predictor from the predictor model.

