Part B is a randomized, double-blind, placebo-controlled, parallel group, dose-finding investigation to evaluate the efficacy, safety, and immunogenicity of izokibep in subjects with moderate to severe HS. Subjects will complete up to a 28-day screening period, followed by a 16-week double-blind treatment period. At completion of the Week 16 visit procedures, subjects randomized to placebo will be switched to active treatment in a blinded manner for the Week 16 dose through Week 30 (Q2W dose group) or Week 31 (QW dose group). Subjects randomized to izokibep will remain on the same dose through Week 30 (Q2W dose

group) or Week 31 (QW dose group). After their respective treatment periods, all subjects will enter a follow-up period that includes 2 visits to be completed at Week 39 and Week 45. For subjects that early terminate the follow-up visits should be completed 8-weeks (\pm 5 days) and 14 weeks (\pm 5 days) after the last dose of study drug.

Approximately 170 subjects will be randomized into 1 of 4 groups in a 1:1:2:2 ratio as follows:

- Group 1 (n = 28-29): placebo SC QW from Day 1 (Week 0) to Week 15, then izokibep SC 160 mg QW from Week 16 to Week 31.
- Group 2 (n = 28-29): placebo SC Q2W from Day 1 (Week 0) to Week 14, then izokibep SC 160 mg Q2W from Week 16 to Week 30.
- Group 3 (n = 56-57): izokibep SC 160 mg QW from Day 1 (Week 0) to Week 31.
- Group 4 (n = 56-57): izokibep SC 160 mg Q2W from Day 1 (Week 0) to Week 30.

Randomization will be stratified by any prior biologic/Janus Kinase (JAK) inhibitor used for HS (Yes/No) and Hurley Stage (II or III).

Subjects will complete study assessments according to the study visits outlined in the SoA in the protocol. Day 1 corresponds to the first dose of study drug. All subsequent visits will be scheduled based on the Day 1 visit.

Subjects in the QW dosing groups (Group 0 [Part A], Groups 1 and 3 [Part B]) will have study visits at screening, Day 1 (Week 0), and at Weeks 1, 2, 3, 4, 8, 12, 13, 14, 15, 16, 17, 20, 24, 28, and 32 as well as at the follow-up visits.

Subjects in the Q2W dosing regimens (Groups 2 and 4 in Part B) will have study visits at screening, Day 1 (Week 0), and at Weeks 2, 4, 8, 12, 14, 16, 18, 20, 24, 28, and 32 as well as at the follow-up visits.

Subjects assigned to placebo SC QW and placebo SC Q2W will be grouped into a single placebo group for comparison to each dosing regimen of izokibep for Part B. The primary endpoint will be assessed at Week 16.

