2.3. Sample Size and Power

In Part A, a minimum of 20 subjects and up to 30 subjects will be enrolled. With the minimum of 20 subjects enrolled if the true HiSCR response rate is 50%, an observed rate of 30% to 70% will be observed with 95% probability. Conversely, an observed response rate of 25% or lower suggests that the true rate is < 50% and an observed rate of 75% or higher suggests that the true rate is > 50%, based on limits of a two-sided 95% CI.

For Part B, power calculations were reported in protocol 21102 version 3.0, dated 26 April 2023, for the original primary endpoint of HiSCR50 and not for the updated primary endpoint of HiSCR75. Using the updated primary endpoint of HiSCR75, the comparisons of a regimen of izokibep to placebo will have approximately 55 subjects in each izokibep regimen compared to approximately 55 subjects on placebo (QW and Q2W combined). In prior studies of adalimumab in a similar patient population, a HiSCR75 response rates of 10% to 15% was observed with placebo compared with response rates of 25% to 35% with adalimumab. If true response rates with placebo and izokibep are 15% and 40%, respectively, this study will have approximately 80% power to reject the null hypothesis of equal response rates. This calculation was made in SAS® using the POWER procedure on an unstratified test of binomial proportions.

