6.1. General Principles

All data processing, summarization, and analyses will be performed using

's SAS Environment/Version 9.4 (or later) of the SAS[®] statistical software package. When data are collected both in IRT and EDC, all data for summaries and analyses will come from the EDC unless it is specifically stated that a particular data point will come from IRT.

The default summary statistics for quantitative variables will be the number of observations (n), mean, standard deviation (SD), median, minimum (min), and maximum (max), for those subjects with data.

For qualitative variables, the number (n) and percentage (%) of subjects with non-missing data per category will be the default summary presentation, and where appropriate and present, the number of missing values as a "Missing" category. The number of subjects in the analysis population will be used as denominator for percentages calculation, unless stated otherwise in TFLs mock shell(s).

The treatment group labels and presentation order are given below:

Part A	1

Full treatment group label:	Short treatment group label:	Treatment group ordering:
Open label izokibep 160 mg QW from Day 1/week 0 to Week 31	Open label Izokibep 160 mg QW	1

Part B

Full treatment group label:	Short treatment group label:	Treatment group ordering:
Placebo SC Q2W Week 0 to Week 14;		
Izokibep SC 160 mg Q2W Week 16 to Week	Placebo Q2W-	
30	Izokibep Q2W	1
Placebo SC QW Week 0 to Week 15; Izokibep	Placebo QW-	
SC 160 mg QW Week 16 to Week 31	Izokibep QW	2

Placebo SC QW Week 0 to Week 15; Izokibep SC 160 mg QW Week 16 to Week 31		
or		
Placebo SC Q2W Week 0 to Week 14; Izokibep SC 160 mg Q2W Week 16 to Week 30	Combined Placebo - Izokibep QW or Q2W	3
Izokibep SC 160 mg Q2W Week 0 to Week 30	Izokibep SC 160 mg Q2W	4
Izokibep SC 160 mg QW Week 0 to Week 31	Izokibep SC 160 mg QW	5

All statistical comparisons will be made using two-sided tests at the $\alpha = 0.05$ significance level unless specifically stated otherwise. All null hypotheses will be of no treatment difference. All alternative hypotheses will be two-sided.

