6.6. Efficacy

Primary, secondary and exploratory endpoints will be presented by study part, timepoint and, for Part B, randomized treatment group. Observed data for binary endpoints, with NRI, will be presented with 2-sided 95% confidence intervals calculated using asymptotic Wald method. Observed data for continuous endpoints, with no imputation for missing values, will be presented with 2-sided confidence intervals calculated using normal approximations.

No statistical hypotheses will be tested in Part A of this study.

Hypotheses tested using data from Part B will be adjusted to control the family-wise error rate in the strong sense at $\alpha = 0.050$, two-sided. An adjustment of 0.0001 will be made to account for the unblinded data summaries reviewed by the DMC. The hypotheses will therefore be tested at $\alpha = 0.0499$.

The statistical comparisons in Part B for the primary efficacy endpoint and the secondary endpoints, all at Week 16, will be carried out in sequential order. The primary endpoint, comparing izokibep dosed QW to placebo dosed QW or Q2W, will be tested first, with significance concluded if p < 0.0499. If significant, the primary endpoint, comparing izokibep dosed QW or Q2W will be tested next, with significance concluded if p < 0.0499. If significant, the primary endpoint, comparing izokibep dosed Q2W to placebo dosed QW or Q2W will be tested next, with significance concluded if p < 0.0499. Testing of secondary endpoints will only be carried out if all prior tests, including both tests of the primary endpoint, first show significance with p < 0.0499. As long as all prior tests are significant, testing will proceed in the following order:

- The first secondary endpoint, proportion of subjects who experience ≥ 1 disease flare through 16 weeks of treatment, comparing izokibep dosed QW to placebo dosed QW or Q2W.
- The first secondary endpoint, proportion of subjects who experience ≥ 1 disease flare through 16 weeks of treatment, comparing izokibep dosed Q2W to placebo dosed QW or Q2W.
- The second secondary endpoint, achieving AN count of 0, 1, or 2 at Week 16 among subjects with baseline Hurley Stage II, comparing izokibep dosed QW to placebo dosed QW or Q2W.
- The second secondary endpoint, achieving AN count of 0, 1 or 2 at Week 16 among subjects with baseline Hurley Stage II, comparing izokibep dosed Q2W to placebo dosed QW or Q2W.

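### The tipping-point analysis reports how often single fills reject but gives no pooled test and no rule for a changed conclusion, so the tipping boundary is undefined

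*SAP*

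**What the plan says.** SAP 6.6.2 describes the tipping-point analysis as a robustness check on the primary result, meant to show how far assumed response rates among subjects with missing data would have to move before the conclusion altered. The assumed rates start from the observed Week 16 rates and move in steps of 0.02, separately in each arm. For each pair of rates, every missing outcome is drawn at random as response or non-response, 1000 times, and the primary stratified analysis is run on each completed data set. Then "the probability that the null hypothesis of equal response rates is rejected will be reported for each set of 1000 imputed response rates". A graph shades this share in five bands, with edges at 95%, 80%, 50% and 20%. The text gives no limits for the grid and does not say which share or band means that the conclusion has changed.

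The separate placebo-based multiple imputation in the same section does combine its data sets: "The final inference on treatment difference is conducted from the multiple datasets using Rubin's combining rules". The decision rule for the primary test is in SAP 6.6, "with significance concluded if p < 0.0499", and SAP 6.1 adds that "All alternative hypotheses will be two-sided".

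**The concern.** The primary analysis counts every missing Week 16 outcome as non-response. The tipping-point analysis is the one that varies the assumed response rate independently by arm, so it should show which assumptions would overturn the primary result.

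Its output is not on the scale of the decision rule. Each fill is tested as though its random outcomes had been observed, so the standard error carries no between-imputation component. The share of fills that reject is not a p-value and has no fixed relation to 0.0499. With no threshold named in advance, a reader may take the conclusion as lost when the share falls below 95%, 80% or 50%. That choice could be made after unblinding, in a study intended as one of two to support an efficacy claim.

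**Working it through.** **The plan's nearest figure.** The tipping-point text states no numerical result. The closest stated figure is the power: "If true response rates with placebo and izokibep are 15% and 40%, respectively, this study will have approximately 80% power", obtained "using the POWER procedure on an unstratified test of binomial proportions". With 55 per arm and two-sided alpha 0.0499, Fisher's exact test gives 79.8% and a continuity-corrected normal approximation 78.6%. Both reproduce it.

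**Inputs from the documents.** Two-sided alpha is 0.0499, so the critical |z| is 1.961. For arm size, "Approximately 170 subjects will be randomized into 1 of 4 groups in a 1:1:2:2 ratio": 170 × 2/6 = 56.7 per izokibep arm, and 170 × (1+1)/6 = 56.7 for pooled placebo, so 57 against 57.

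**Assumed inputs.** The documents give no missing-data rate. I take 9 of 57 missing per arm (16%), observed responders 16/48 (active) and 7/48 (placebo), active missing filled at its observed rate 1/3, and placebo missing filled at a rate q that is varied. The test is unstratified for transparency.

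**Starting point.** Under non-response imputation the difference is 16/57 − 7/57 = 0.158. The SE is √(0.2807×0.7193/57 + 0.1228×0.8772/57) = 0.0737, so z = 2.14 and p = 0.032. There is a significant result to tip.

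**Pooling.** Let U be the average squared SE over fills, B the between-fill variance and T = U + (1 + 1/1000)B. At q = 0.26:
- Active rate (16 + 3)/57 = 0.3333; placebo rate (7 + 2.34)/57 = 0.1639; difference 0.1695 before rounding.
- U = 0.3333×0.6667/57 + 0.1639×0.8361/57 − B/57 = 0.00628; SE 0.0793. This is what each single-fill test uses on average.
- B = 9 × (0.3333×0.6667 + 0.26×0.74)/57² = 0.00115; SD 0.0339.
- T = 0.00628 + 0.00115 = 0.00743; SE 0.0862, about 9% above 0.0793.
- z = 0.1695/0.0862 = 1.966; p = 0.049.

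The rows below weight all 10 × 10 possible pairs of fill counts by their binomial probabilities, so they carry no simulation error.

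| Placebo fill rate q | Difference | Single-fill SE | Pooled SE | Pooled p | Fills that reject |
|---|---|---|---|---|---|
| 0.21 | 0.177 | 0.0787 | 0.0852 | 0.037 | 79% |
| 0.26 | 0.170 | 0.0793 | 0.0862 | 0.049 | 70% |
| 0.28 | 0.166 | 0.0795 | 0.0866 | 0.055 | 66% |
| 0.36 | 0.154 | 0.0804 | 0.0878 | 0.080 | 49% |

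The pooled test tips just above 0.26. A reader using the 80% edge puts the boundary near 0.21; one using the 50% edge puts it near 0.36. That is a spread of 0.36 − 0.21 = 0.15 in the assumed rate.

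**Stratified check.** This used 57 per arm, four equal strata, the Mantel-Haenszel risk difference with the Sato variance and 1000 simulated fills. Placebo missing were filled at the placebo observed rate and the active fill rate was shifted from its own observed rate.
- 9 missing per arm, 17/48 versus 8/48: pooled p crosses between shifts of −0.12 (p = 0.047, 72% reject) and −0.14 (p = 0.052, 67%). The 80% edge is passed at −0.04 and the 50% edge at −0.24, a spread of 0.20.
- 11 missing, 17/46 versus 7/46: it crosses between −0.30 (p = 0.047, 71%) and −0.32 (p = 0.054, 63%).
- 6 missing, 18/51 versus 8/51: it never crosses. At an active fill rate of about 0.01, p = 0.046, yet only 77% of fills reject.

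**Sensitivity.** With observed rates of 34% and 14% instead of 16/48 and 7/48, less than one responder different in each arm, z is 0.1747/0.0868 = 2.01 at q = 0.30 and 0.1684/0.0875 = 1.93 at q = 0.34. The crossing moves to between 0.30 and 0.34.

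**The case against.** Several stronger readings are tempting and do not hold.

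- A reader might infer that the analysis never shows where the conclusion changes. It can bracket the change: the share is reported for every scenario in 0.02 steps, and the bands apply only to the graph. A number without a threshold still does not say which scenarios overturn the result.
- A reader might infer that imputation variance is ignored altogether. It is missing from each test's standard error, but fill-to-fill variation is what produces the rejection share.
- A reader might infer that the method flatters the result. That holds only at the 50% edge. At the 80% or 95% edge the map is stricter than the pooled test, as the case with 6 missing shows.
- A reader might take this for the only missing-data check, or take the use of Rubin's rules in the next paragraph as a contradiction. The placebo-based multiple imputation is a second check with pooled inference, and it is a different, model-based method.

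The strongest technical objection is that Rubin's rules presume imputation parameters drawn from a distribution, whereas here the rate is fixed within a scenario. If the rates were true constants, the repeated-sampling SD of the averaged difference would be about 0.072, below both the single-fill SE and the pooled SE. But the SAP sets each rate relative to the observed rate, which itself varies from sample to sample. Under that reading the repeated-sampling SD is 0.086 against Rubin's 0.087, so pooling is about right for the analysis as written.

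**Conclusion.** The point holds as a cheap improvement. The tipping-point analysis has no pooled test and no criterion for a changed conclusion, so its boundary is undefined. The fault is ambiguity, not bias in a known direction.

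In the illustrations that cross, the pooled tipping point lies at roughly 63-72% rejection, inside the 50-80% band and on no band edge. The choice between the 80% and 50% edges moves the apparent boundary by 0.15 in the unstratified example and by 0.20 in the stratified example with 9 missing per arm. The 8-9% gap in standard error belongs to the unstratified example. All of these sizes rest on assumed missing-data rates and observed counts, and the crossing shifts noticeably with less than one responder per arm. The absence of a pooled test and of a threshold does not depend on those assumptions. The primary non-response analysis and the 0.0499 level are untouched.

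**What to change.** Amend the tipping-point paragraph of SAP 6.6.2 before unblinding:

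- At each grid point, combine the 1000 filled data sets by Rubin's rules, using the primary stratified risk difference and its standard error. Report the pooled difference, 95% CI and p-value.
- Define the tipping boundary as pooled p = 0.0499 and draw it on the graph.
- State the grid limits. Extend the grid far enough to reach the boundary, or report that it is not reached.
- Keep the rejection-share shading, if wanted, as a secondary display.
- Optionally add the point where both fill rates are zero, which ties the map to the primary non-response result. Steps of 0.02 from the observed rates will usually miss it: 7/48 = 0.1458, less seven steps, leaves 0.0058.

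The cost is SAP wording and a little more programming on data sets already planned. Nothing in the primary test or the alpha changes.

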Multiple imputation will be used to impute data for subjects with missing data. The multiple imputation process will be the same the supplementary analysis defined in section 6.6.2 for HiSCR75, except that draining fistula counts do not play a role in flare and will therefore not be imputed when missing. Subjects with missing AN counts at any scheduled visit (week 4, week 8, week 12 and/or week 16) will have their abscess and inflammatory nodules counts imputed (separately) for each visit with missing data. The imputed counts will be summed and compared to criteria for flare. If the observed or imputed value at any visit meets the definition of flare, the subject will be counted as having a flare; otherwise, the subject will be counted as not having a flare. A total of 100 imputations will be imputed to form the complete data set with a pre-specified seed (3617627) to ensure reproducibility. These multiple imputed data sets are then analyzed by using the same method for the primary analysis for complete data as specified in Section 6.6.1. The final inference on treatment difference is conducted from the multiple datasets using Rubin's combining rules⁷. Other imputation, fully conditional specification method may be implemented if the multiple imputation model does not converge.

Note that NRI will not be used for the primary analysis of flare. The number of subjects with missing data may be larger than the number of subjects who experience a flare, so using NRI may result in an analysis dominated by missing data. A supportive analysis, described below, will be reported using NRI.

6.6.3.2. Hurley Stage II Subjects Achieving AN Count of 0, 1, or 2 at Week 16

The secondary endpoints of percentage of subjects with baseline actual Hurley Stage II who achieved AN count (including those lesions that had interventions before Week 16 and were no longer present at Week 16) of 0, 1, or 2 at Week 16 will be analyzed analogously to the primary endpoint. The statistical null and alternative hypotheses to be used to assess these objectives are:

H₀: $\pi_{ABY} - \pi_{PBO} = 0$ H_A: $\pi_{ABY} - \pi_{PBO} \neq 0$

where π_{ABY} and π_{PBO} are the proportion achieving AN count of 0, 1, or 2 at Week 16 among subjects randomly assigned to receive izokibep and placebo, respectively. One set of hypotheses will be tested for each dosing frequency of izokibep.

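### The imputation of intermittently missed lesion counts leaves out the later counts that are observed; if visits are missed at random, the alpha-controlled flare analysis imputes too many flares at those visits

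*SAP*

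**What the plan says.** SAP 6.6.2 (Multiple Imputation) has two steps. The first uses MCMC to make the missingness pattern monotone; the second imputes what remains missing at Weeks 4, 8, 12 and 16.

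- **Week 4 gap, MCMC step.** The predictors are baseline abscess, nodule and draining fistula counts, age and BMI. They apply "for nonmonotone missingness at Week 4 (missing at Week 4 but available at a later timepoint".
- **Gaps after Week 4, MCMC step.** "MCMC predictors in the regression model for missing values after Week 4 will be all of these variables, plus counts of abscess", with nodule counts and "draining fistula (continuous) at prior scheduled assessments".
- **Order.** "Data will be processed sequentially by repeatedly calling SAS® PROC MI to impute missing outcomes at Week 4, 8, 12, and 16".
- **Data used for the fit.** "Missing HiSCR75 values in both the placebo group and two izokibep groups will be imputed using observed data from the placebo group only".

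SAP 6.6.3.1 carries this over to the main flare analysis: "The multiple imputation process will be the same the supplementary analysis defined in section 6.6.2 for HiSCR75". The one exception is that fistula counts are not imputed. A subject has a flare if any single visit, observed or imputed, shows a rise in AN count of at least 25% and at least 2 over baseline. Flare is in the alpha-controlled sequence in both documents (Protocol 9.1.1, SAP 6.6). Protocol 9.3.3 requires multiple imputation for flare but names no predictors.

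**The concern.** Using prior visits only is right for dropout, where no later data exist. An intermittent gap is different, because the count after the gap is known and informative. As listed, a subject whose counts fell well below baseline at Weeks 8, 12 and 16 has Week 4 imputed as though nothing were known after Day 1.

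The list also conflicts with the purpose of the step. If only baseline and earlier visits enter, the visit being imputed is the last variable in the model and the pattern is already monotone. MCMC then has nothing to enforce. It is useful here only if later visits are in the model.

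Flare is sensitive to this because one imputed visit decides the subject's status. A subject with an observed flare counts as a flare anyway, so the imputation matters only when all observed visits are flare-free. For those subjects the omitted later counts lower the chance of a flare at the gap. At stake are the flare estimate, some power for a test in the fixed sequence, and the tests that follow it.

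**Working it through.** **Stated figures.** Neither document gives a flare rate, a missed-visit rate or a power for flare, so there is no flare figure to reproduce. The only design figure is HiSCR75 power of about 80% for 15% against 40% with 55 per group. Fisher's exact test gives 79.8% (the plain chi-square gives 84.5%). This point does not depend on it.

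**Step 1: one gap.** Assumptions: median baseline AN count 11; log change from baseline with SD 0.6; mean −0.2 on placebo and −0.6 to −0.9 on izokibep; between-visit correlation 0.5–0.8; model fitted on placebo, as the SAP says.

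At a baseline of exactly 11, the 25% rule binds (11 × 1.25 = 13.75, above 11 + 2 = 13). The chance of a flare at Week 4 given baseline only is P(Z > (ln 1.25 + 0.2)/0.6) = P(Z > 0.705) = 0.24. Averaged over a spread of baselines, where the 2-lesion rule binds at low counts, it is 0.23. Among subjects with no flare at the observed visits:

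| Gap | As written | All other visits used | True |
|---|---|---|---|
| Week 4, placebo | 23% | 7–13% | 7–13% |
| Week 4, izokibep | 23% | 2–9% | 1–5% |
| Week 8 or 12, izokibep | 3–11% | 1–6% | 1–4% |

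**Step 2: effect on the arm difference.** Excess flares per unit gap rate = share with no observed flare × (imputed − true). With exchangeable correlation 0.7 and izokibep mean −0.9:

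- izokibep: 0.94 × (0.230 − 0.012) = 0.205
- placebo: 0.62 × (0.230 − 0.065) = 0.102

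If 5–10% of subjects miss only Week 4, izokibep rises by 1.0–2.1 points and placebo by 0.5–1.0. The difference shrinks by about 0.5–1 point. With an izokibep mean of −0.6 it shrinks by 0.35–0.7 points.

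**Step 3: role of the placebo-only fit.** Keep the predictor list as written but fit the model on the subject's own arm. The imputed Week 4 flare rate on izokibep falls from 23% to 3–8%. The excess per unit gap rate becomes 0.008–0.043 on izokibep and 0.058–0.100 on placebo, so the difference would widen.

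**Step 4: whole trial.** Abscess and nodule counts were simulated at Weeks 0 to 16 (60,000 per arm), with 5% missed at random at each of Weeks 4, 8 and 12, so 1 − 0.95³ = 14% of subjects have a gap. Ranges cover three within-subject correlations. Power is at 170/3 = 56.67 per group and alpha 0.0499.

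| | Complete data | As written | Later counts added |
|---|---|---|---|
| Izokibep, subjects with a gap | 13–19% | 25–33% | 17–26% |
| Placebo, subjects with a gap | 39–45% | 46–52% | 41–48% |
| Izokibep, whole arm | 13.8–19.0% | 15.5–21.0% | 14.2–20.0% |
| Power | 87–89% | 84–86% | 85–88% |

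At 10% missed per visit, power is 79–83% as written and 83–87% with later counts. In a lower-flare case at 5% missed, placebo is 22.7% true and 23.2% as written, and izokibep 6.5% and 7.4%. The difference goes from 16.2 to 15.8 points.

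At medium correlation, izokibep subjects with a gap go from 16% true to 30% as written. Adding later counts gives 21%, and fitting on the own arm as well gives 17%.

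**Step 5: checks on direction.** With no treatment effect, the rule as written rejected in 4.8% (5% missed) and 3.7% (10% missed) of 1,200 simulated trials each. If a flaring visit is missed 30% of the time and others 5%, placebo subjects with a gap have a true rate of 46%; the rule gives 39%, and adding later counts gives 36%.

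The simulations are unstratified and ignore unscheduled visits and the antibiotic rule.

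**The case against.** Three arguments on the other side have force.

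- **The placebo-only fit is a declared choice.** Drawing izokibep subjects toward placebo is what such a rule is meant to do, so some bias toward no difference is intended. This stands. It does not explain why a subject's own observed later counts are left out, and placebo subjects are affected too.
- **The programmer may put all visits into one joint MCMC call.** Later counts would then be used. The SAP's predictor list says otherwise, so the text needs correcting under either reading.
- **The effect is small and other analyses surround it.** With about 57 per group and, say, 40% against 14%, the standard error of the difference is √(0.40 × 0.60/57 + 0.14 × 0.86/57) = 0.080, so a 1-point shift is about an eighth of it. SAP 6.6.4 adds flare analyses with missing counted as flare and as no flare. Those would help show the influence of imputation, but they do not correct the alpha-controlled test.

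A reader might also infer that omitting later counts shrinks the treatment difference by itself. Step 3 shows that it does not: the shrinkage needs the placebo-only fit as well.

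**Conclusion.** The point holds as a defect in the stated predictor list. Followed literally, SAP 6.6.2 discards observed counts in exactly the cases it defines by their existence, and SAP 6.6.3.1 carries this into the main flare analysis.

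If visits are missed at random, flare is imputed too often among subjects with a gap and no observed flare. With the placebo-only fit, the excess is larger on izokibep. The flare difference then shrinks by about 0.5–1 point when 5–10% miss Week 4, and power falls by about 1–3 points at 5% missed per visit. These sizes rest on assumed flare rates, gap rates and correlations.

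Three stronger readings are not supported. Flares are not over-counted under every missingness mechanism, since placebo flares can be under-counted when flaring visits are missed more often. The simulations show no inflation of type I error. The primary HiSCR75 analysis is untouched, because it uses non-response imputation at Week 16 and not this model.

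**What to change.** In SAP 6.6.2 and 6.6.3.1, state that the MCMC step for intermittent gaps includes abscess and inflammatory nodule counts at all scheduled visits (Weeks 4, 8, 12 and 16, earlier and later than the gap) together with the baseline variables. Keep prior visits only for the monotone dropout step that follows. Apply the same rule to the fully conditional specification fallback, whose predictors are not stated.

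The cost is one sentence and a longer variable list in the MCMC call. It needs no new data and does not change alpha. It removes much of the izokibep excess but not the part due to the placebo-only fit, and it does not protect against visits being missed because of a flare.
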